#### 9.8 Vital Signs and Physical Evaluations

Vital sign measurements included systolic blood pressure, diastolic blood pressure, heart rate and oral temperature, along with height and weight at Screening. Vital signs were assessed at Screening, Day 1, Day 8, Day 29 and Day 85. Systolic Abnormalities in systolic and diastolic blood pressure will be tabulated by grade, visit and treatment group (Table 14.3.5.1). Diastolic and systolic blood pressure and heart rate will be summarized over time graphically using box plots for participants in the FA population (Figure 14.3.5.2). Listings of all individual vital sign measurements will be provided in Listing 16.2.9.1.

Physical Examinations were performed at Screening, Day 1, Day 8, Day 29, and Day 85. Any abnormal or change in physical examination data from Day 1 will be listed for each participant by visit and treatment group. The following body systems will be assessed: HEENT, Skin, Back, Neck, Chest, Abdomen, Neurological, and Musculoskeletal (Listing 16.2.9.2).

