#### 8.3. Definitions

#### 8.3.1. Adverse Event (AE)

An adverse event is any untoward medical occurrence in humans, whether or not considered vaccine related, that occurs after the vaccination during the conduct of a clinical trial. Any change from baseline assessment of clinical status, ECGs, routine laboratory tests, X-rays, physical examinations, etc., that is considered clinically significant by the PI is considered an AE.

**Suspected adverse drug reaction** is any AE for which there is a reasonable possibility that the vaccine caused the AE. A reasonable possibility implies that there is evidence to suggest that the study product caused the event.

Adverse reaction is any AE caused by the vaccine.

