#### 3.3 Study Definitions and Derived Variables

The following definitions and derivations will be used in this study:

- The baseline value will be defined as the last value obtained prior to the vaccination of study product.
- The reference day will be the day of vaccination and will be referred to as Day 1.
- Study days prior to vaccination will be calculated by taking the date minus the vaccination date (reference day).
- Study days occurring on or after the date of vaccination will be calculated by taking the date minus the vaccination date (reference day) and adding 1.
- Age will be calculated from the date of enrollment and will be presented in whole years (truncated integer).
- The calculations for GMTs will be performed by taking the anti-log of the arithmetic mean of the natural log-transformed titers.
- Fold increase will be calculated as the ratio of:  $\frac{post-immunizationrSBAtiter}{pre-immunizationrSBAtiter}$
- Seroconversion (4-fold response) will be defined as the following:
  - $\circ$  For participants with a pre-vaccination rSBA titer < 8, a post-vaccination titer  $\geq 32$ ;
  - For participants with a pre-vaccination rSBA titer ≥ 8, an increase in rSBA titer of at least
     4 times the pre-vaccination titer.
- Seroprotection will be defined as a rSBA titer of  $\geq 8$  and  $\geq 128$ .
- Prior medications are those medications that started and stopped prior to vaccination.

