#### 9.4 Adverse Events

All safety analyses will be presented using the FA population.

Any medical condition that is present at the time that the participant is screened will be considered baseline and not reported as an AE, unless it worsens in severity or increases in frequency during the study. A treatment-emergent adverse event is one that is observed after baseline or worsens in severity or increases in frequency during the study. Solicited and unsolicited adverse events (AEs) will be analyzed separately. When calculating the incidence of AEs (i.e., on a per participant basis), each participant will be counted once and any repetitions within a participant will be ignored; the denominator will be the total population size. For tables summarizing severity, the severity will be summarized as the maximum severity experienced by that participant for a particular AE or symptom. All adverse events reported will be included in the summaries and analyses.

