#### 9.7 Clinical Laboratory Evaluations

Safety clinical laboratory evaluations will be performed at Screening and at Day 8 at the site's designated laboratory and will include: hemoglobin (HgB), white blood cells (WBC), platelet counts, alanine transaminase (ALT), albumin, total bilirubin, and creatinine. In addition, screening laboratory tests will include serum HCG pregnancy tests, for females of childbearing potential only, and screening for HIV, HCV and HBV.

The distribution of laboratory results by severity, scheduled study day and treatment group will be presented in Table 14.3.4.1 for any laboratory parameter and each individual laboratory parameter. The observed and change from screening measurements will be summarized using descriptive statistics including mean, standard deviation, median, 25th and 75th percentiles, minimum and maximum values by scheduled study day, for each laboratory parameter in Table 14.3.4.2. Graphical presentation of changes in laboratory values will be presented using box plots as depicted in Figure 14.3.4.3 for each laboratory parameter. Unscheduled or repeated follow-up tests for medical or safety reasons will be listed and included in the maximum post-baseline row on the summary tables, but will otherwise be excluded from tabular and graphical summaries.

Participant visits with abnormal laboratory results, Grade 1 severity or higher, will be presented in Table 14.3.4.4.

Listings of all individual clinical laboratory results will be provided by hematology, biochemistry and serology (Listings 16.2.8.1-16.2.8.3, respectively). Results meeting the protocol defined toxicity of Grade 1 or higher will have their grade provided in parentheses after the result.

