FIGURE 14.3.4.3: Laboratory Results by Scheduled Visits: Mean Value at Baseline and Day 8 by Laboratory Parameter and Treatment Group - Full Analysis Population

Note: Continue for all laboratory tests: Platelet Counts (cells/mm³), White Blood Cells (cells/mm³), Alanine Aminotransferase (ALT) (U/L), Creatinine (mg/dL), Total Bilirubin (mg/dL), Albumin (g/dL).

TABLE 14.3.4.4: Listing of Abnormal Laboratory Results

Participant ID	Treatment Group	Sex	Age (years)	Planned Time Point	Actual Study Day	Laboratory Parameter (Units)	Result (Severity)	Relationship to Treatment	If Not Related, Alternate Etiology	Action Taken with Study Treatment	Participant Discontinued Due to Result?

[figure not shown]
[Implementation Note: This listing only includes abnormal laboratory results. A complete listing of all laboratory results is included in the listings document. In the Laboratory Parameter column, indicate the units after the parameter, e.g., Hemoglobin (g/dL). The grade will be included in parentheses after the result, e.g., 16.2 (Grade 1).]

TABLE 14.3.5.1: Distribution of Vital Signs by Grade, Study Visit, and Treatment Group - Full Analysis Population

			Adjuvanted	MCV-5 (N=2	XX)				
			Pre-Vaccination (N=X)		Visit 3 (Day 8) (N=X)		Day 29) =X)		Day 85) =X)
Vital Sign Assessment	Grade	n	%	n	%	n	%	n	%
Diastolic Blood Pressure (mm Hg)	Normal	X	XX.X	X	XX.X	X	XX.X	X	XX.X
	Hypertension Grade 1	X	XX.X	X	XX.X	X	XX.X	X	XX.X
	Hypertension Grade 2	X	XX.X	X	XX.X	X	XX.X	X	XX.X
	Hypertension Grade 3	X	XX.X	X	XX.X	X	XX.X	X	XX.X
Systolic Blood Pressure (mm Hg)	Normal	X	XX.X	X	XX.X	X	XX.X	X	XX.X
	Hypertension Grade 1	X	XX.X	X	XX.X	X	XX.X	X	XX.X
	Hypertension Grade 2	X	XX.X	X	XX.X	X	XX.X	X	XX.X
	Hypertension Grade 3	X	XX.X	X	XX.X	X	XX.X	X	XX.X

Repeat for all treatment groups: Non-adjuvanted MCV-5 and Menactra®

FIGURE 14.3.5.2:
Vital Sign Measurements by Scheduled Visits: Mean Values from Baseline to Day 85
by Vital Sign and Treatment Group - Full Analysis Population

Note: Continue for all vital signs: Systolic Blood Pressure (mmHg), Heart Rate (beats/min)

TABLE 14.3.6: Concomitant Medications Summary by Treatment Group - Full Analysis Population

			Study Group	
		Adjuvanted MCV-5	Non-adjuvanted MCV-5	Menactra®
ATC1	Drug name (preferred)	n	n	n
[e.g., ANTIINFECTIVES FOR SYSTEMIC USE ]	[e.g., TRUVADA ]			
Total				

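### SAP Table 14.3.5.1 has no category for low blood pressure and does not compare participants with their own pre-vaccination value

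*SAP*

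**What the plan says.** SAP 4.5.1 names vital signs among the safety variables. SAP 9.8 has them measured at Screening, Day 1, Day 8, Day 29 and Day 85, and plans three outputs.

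- **Table 14.3.5.1.** "Abnormalities in systolic and diastolic blood pressure will be tabulated by grade, visit and treatment group". For both systolic and diastolic pressure the shell has four rows, from Normal to "Hypertension Grade 3". Its columns are Pre-Vaccination, Day 8, Day 29 and Day 85. It has no low row and no missing row.
- **Figure 14.3.5.2.** Box plots of both pressures and heart rate over time, by scheduled visit.
- **Listing 16.2.9.1.** Raw values for each participant, scheduled and unscheduled, with no grade or change column.

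SAP 9.7 plans more for laboratory values: "The observed and change from screening measurements will be summarized using descriptive statistics", and unscheduled or repeat tests are "included in the maximum post-baseline row on the summary tables". The laboratory grade shells carry a Missing column, and most mark direction as low or high.

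Under protocol 8.3.1, a change from baseline that is "considered clinically significant by the PI is considered an AE". The rule in protocol 8.7 that Grade 2 or higher abnormalities are reported as AEs covers laboratory results only.

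**The concern.** A table said to show blood-pressure abnormalities has categories for one direction only. A reader who sees a participant counted as Normal cannot know whether the pressure was normal or low. If low readings are left out instead, the rows will not add to the number assessed, and without a missing row nothing explains the shortfall.

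The counts are also cross-sectional. In a safety review the useful question is how many participants moved to a worse category after vaccination, and separate counts at each visit do not answer it. Readings at unscheduled visits, which under protocol 5.3 may be held to diagnose or manage a finding or AE, have no column in the table and no place in the scheduled-visit plots.

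This is the only planned tabulation of graded blood pressure, in a first-in-human trial whose primary objective is safety. What is at stake is how easily a change in blood pressure could be seen in the report. The data themselves are collected.

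**Working it through.** The plan states no figure for this point, so there is none to reproduce. The check has two parts.

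**1. Where can a low reading go?** The rows for each pressure are Normal and Hypertension Grades 1, 2 and 3. A low reading fits none of the hypertension rows, so it is either counted as Normal or not counted. The SAP does not define Normal and does not say which happens. The number of scheduled readings exposed to this ambiguity is:

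- participants per arm: 20 (SAP 4.1)
- post-vaccination visits in the table: 3 (Days 8, 29 and 85)
- readings per arm for each pressure: 20 × 3 = 60

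The documents give no basis for saying how many of the 60 would be low.

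**2. What do separate counts say about new cases?** Let n = 20, with a participants in a hypertension grade before vaccination and b at a later visit. If k participants are graded at both times, the newly graded number b − k. Since k must lie between max(0, a + b − n) and min(a, b), the newly graded number lies between max(0, b − a) and min(b, n − a). The counts below are assumed for illustration.

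| Before (a) | After (b) | Fewest new | Most new | Share of arm |
|---|---|---|---|---|
| 2 | 2 | 0 | 2 | 0% to 10% |
| 4 | 4 | 0 | 4 | 0% to 20% |
| 4 | 6 | 2 | 6 | 10% to 30% |
| 6 | 6 | 0 | 6 | 0% to 30% |
| 6 | 8 | 2 | 8 | 10% to 40% |
| 8 | 8 | 0 | 8 | 0% to 40% |

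A worst post-vaccination count cannot be recovered from the visit columns either. With 6 of 20 graded at each of the three visits, the number graded at least once lies between 6 (the same participants each time) and 6 + 6 + 6 = 18 (different participants each time). A shift table would replace these ranges with exact counts.

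**The case against.** The strongest reply is that one table is not the whole report. Listing 16.2.9.1 gives every participant's pressures by study day, unscheduled readings included, and 60 participants can be read one by one. The box plots show low values at group level. Clinically significant changes are AEs, and SAP 9.4 separates new from old there: "A treatment-emergent adverse event is one that is observed after baseline or worsens in severity or increases in frequency during the study". The shell for Table 14.3.1.7 even carries an example footnote about an AE of increased blood pressure, though that may be template text. All of this stands, and it limits the point. It does not close the gap: the listing leaves the reader to grade and pair readings by hand, the plots do not follow individuals, and AE capture depends on the investigator's judgement.

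The laboratory grade tables have no baseline-by-worst shift, so that part of the fix goes beyond the SAP's own laboratory standard. The worst post-baseline summary does not.

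A reader might infer more than the documents support:

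- **That low readings are shown as Normal.** This is one of two possibilities; omission is the other.
- **That new abnormalities cannot be identified at all.** This is true of the table, not of the listing or the AE data.
- **That Grade 4 or heart-rate rows are wrongly missing.** The content of protocol Appendix II is not in the text available for review, and protocol 8.4 does not say that every parameter has four grades. The albumin shell also stops at Grade 3.
- **That abnormal baseline readings are to be expected.** The entry criteria set no numeric blood-pressure limit, but they require health on history and physical examination and exclude clinically significant cardiovascular abnormality. Such readings are possible; their frequency is unknown.
- **That a primary endpoint is affected.** The primary endpoints are solicited reactions, unsolicited AEs and SAEs.
- **That a low row would capture immediate post-injection hypotension.** The scheduled 60-minute check in protocol 5.2.4 records temperature and reactions, not blood pressure.

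**Conclusion.** The point holds in a limited form. Table 14.3.5.1 has no category for low systolic or diastolic pressure, so a low reading is either counted as Normal or left out, and the SAP does not say which. The table supports a group-level comparison with the pre-vaccination column, but it cannot give the number of participants newly abnormal or worsened, and no vital-sign summary includes unscheduled readings. Those cases have to be found in the raw listing or in AE reports.

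The structural finding rests only on the table shell and SAP 9.7 and 9.8. The illustrated ranges, such as 0 to 6 of 20, rest on assumed counts and show what the layout leaves open; they predict nothing about the trial. Severity is minor: no endpoint, test or sample-size statement changes.

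**What to change.** Revise Table 14.3.5.1 as follows.

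1. Add a low-reading category and a missing category for each pressure, so that Normal excludes low values. Use the grades in protocol Appendix II where that scale defines them, and add Grade 4 or heart-rate rows only if it does.
2. Add a worst post-vaccination column that includes unscheduled visits, in line with SAP 9.7 for laboratory values.
3. Add, by arm, a shift of worst post-vaccination category against baseline category, with the number of participants whose category worsened. State that the pre-vaccination value follows SAP 3.3: "The baseline value will be defined as the last value obtained prior to the vaccination of study product". Both Screening and Day 1 are measured, and the shell does not say which it uses.

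The change needs a sentence or two in SAP 9.8 and one revised shell. All readings are already collected, and no procedure or clinical rule changes. The downside is one more small table to program and read. Protocol 7.1 has the SAP final before database lock and unblinding, so the revision belongs before then.

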#### 9.9 Concomitant Medications

Concomitant medications are those medications taken at the same time or after vaccination. Prior medications are those medications that were started and stopped prior to vaccination. Both prior and concomitant medications will be classified according to a standardized drug code. The use of prior and concomitant medications taken during the study will be summarized by medication name and treatment group (Table 14.3.6).

Individual participant listings will be presented for all prior and concurrent medications (Listing 16.2.10).

#### 10 REPORTING CONVENTIONS

P-values  $\geq$ 0.001 and  $\leq$ 0.999 will be reported to 3 decimal places; p-values less than 0.001 will be reported as "<0.001"; p-values greater than 0.999 will be reported as ">0.999". The mean, standard deviation, and any other statistics other than quantiles, will be reported to one decimal place greater than the original data. Quantiles, such as median, or minimum and maximum will use the same number of decimal places as the original data. Proportions will be presented as two decimal places; values <0.01 will be presented as "<0.01". Percentages will be reported to the nearest whole number; values <1% will be presented as "<1". Estimated parameters, not on the same scale as raw observations (e.g., regression coefficients) will be reported to 3 significant figures.

#### 11 TECHNICAL DETAILS

SAS version 9.3 or above will be used to generate all tables, figures and listings.

## 12 SUMMARY OF CHANGES IN CONDUCT OF THE STUDY OR PLANNED ANALYSES

#### 13 REFERENCES

#### 14 TABLES, FIGURES, AND LISTINGS

#### **GENERAL ASSUMPTIONS:**

#### Implementation Notes:

- All figures presented are sample figures and do not include real study data.
- The number of participants presented are not real study data, but generic examples of how to present the data for the different treatment groups. The number of participants will be dependent upon the data observed in the study.
- The total number of participants for each treatment group are not actual numbers, but generic
  examples of how to present the data for the different treatment groups. The total number of
  participants will be dependent upon the data observed in the study.

#### 14.1 Demographics

**FIGURE 14.1.1: Consort Flow Diagram** Screened Screened Failed N=XXXRandomized Adjuvanted MCV-5 Non-Adjuvanted MCV-5 Menactra® Reasons Excluded from the Reasons Excluded from the Reasons Excluded from the Full Analysis Population Full Analysis Population Full Analysis Population (N=XXX)(N=XXX)(N=XXX)Reason 1 (N=XXX) Reason 1 (N=XXX) Reason 1 (N=XXX) Reason 2 (N=XXX) Reason 2 (N=XXX) Reason 2 (N=XXX) Safety Population Safety Population Safety Population Reasons Excluded from the Reasons Excluded from the Reasons Excluded from the PP Population (N=XXX) PP Population (N=XXX) PP Population (N=XXX) Reason 1 (N=XXX) Reason 1 (N=XXX) Reason 1 (N=XXX) Reason 2 (N=XXX) Reason 2 (N=XXX) Reason 2 (N=XXX) PP Population PP Population PP Population N=XXXN=XXXN=XXX

TABLE 14.1.1: Ineligibility Summary of Screen Failures

Inclusion/ Exclusion Category	Inclusion/Exclusion Criterion	Number of Times Item Marked Ineligible		
Any	Any inclusion/exclusion criterion	X		
Inclusion	Any inclusion criterion	X		
	1. Aged 18 to 45 years	X		
	2. Read, signed, and dated informed consent form	X		
	3. Healthy as established at screening	X		
	4. Lab results fall within the protocol parameters	X		
	5. Ability to understand and comply with study procedures	X		
	6. Agrees to adequate contraception, if applicable	X		
	7. Negative pregnancy test, if applicable	X		
Exclusion	Any exclusion criterion	X		
	1. Previous vaccination against Neisseria meningitidis	X		
	2. Known exposure to Neisseria meningitidis in the past.	X		
	3. History of meningitis or seizures or any neurological or psychiatric disorder	X		
	4. Receipt of other vaccine within 30 days prior or after vaccination	X		
	5. Use of other experimental agents within 30 days prior or after vaccination	X		
	6. History of allergic disease or known hypersensitivity	X		
	7. History of SAE following Tetanus Toxoid, Diphtheria Toxoid or CRM	X		
	8. History of Guillain-Barré syndrome	X		
	9. Confirmed or suspected immunosuppressive or immune-deficient condition	X		
	10. Family History of congenital or hereditary immunodeficiency	X		
	11. Chronic administration of immune-suppressants 6 months before vaccination	X		
	12. Laboratory confirmed Hepatitis B, Hepatitis C, or HIV	X		
	13. Major congenital defects or serious chronic illness	X		
	14. Acute or chronic, clinically significant pulmonary, cardiovascular, hepatic or renal functional abnormality	X		
	15. Known bleeding disorders	X		
	16. Receipt of blood products or immunoglobulin 3 months before vaccination	X		
	17. History or signs of alcohol or substance abuse	X		
	18. Pregnant or breastfeeding	X		
	19. Body Mass Index equal to or above 30	X		
	20. Other conditions	X		
Other	Other Reasons	X		
	Time commitment	X		
	Concern of potential risks	X		
	Number of procedures/blood draws	X		
	Unable to contact participant	X		
	Other	X		

Note: SAE = serious adverse event; HIV = human immunodeficiency virus.

**TABLE 14.1.2: Analysis Populations by Treatment Group** 

	Adjuvanted MCV-5 (N=X)		Non-adjuvanted MCV-5 (N=X)		Menactra® (N=X)		All Participants (N=X)		
Analysis Populations	Reason Participants Excluded	n	%	n	%	n	%	%	n
	Any Reason	X	x.x	X	x.x	X	X.X	х	x.x
Full Analysis Population	Not Randomized	X	X.X	X	x.x	X	x.x	X	x.x
	Randomized but not vaccinated	X	X.X	Х	x.x	X	x.x	X	x.x
	Any Reason	X	X.X	X	X.X	X	x.x	X	X.X
Per Protocol Population	No Valid Immunogenicity Assessment	X	X.X	Х	X.X	X	x.x	X	X.X
	Major Protocol Violation	Х	X.X	Х	X.X	Х	x.x	Х	X.X

N=Number of participants enrolled in the study.

TABLE 14.1.3:
Participant Disposition by Treatment Group

Participant		ted MCV-5 =XX)		nted MCV-5 XX)		actra® =XX)	All Participants (N=XX)	
Disposition	n	%	n	n	n	%	n	%
Screened							xx	
Enrolled/Randomized	XX	100.0	xx	100.0	XX	100.0	xx	100.0
Received Vaccination	XX	XX.X	xx	XX.X	XX	XX.X	xx	xx.x
Completed Visit 3 (Day 8)	XX	XX.X	xx	XX.X	XX	XX.X	xx	xx.x
Completed Visit 4 (Day 29)	xx	XX.X	xx	XX.X	XX	XX.X	xx	XX.X
Completed Visit 5 (Day 85)	XX	XX.X	xx	XX.X	XX	XX.X	xx	XX.X
Completed Follow-up at 6 Months Post-Vacc a	xx	XX.X	xx	XX.X	XX	XX.X	xx	XX.X
Per Protocol population b	XX	XX.X	xx	XX.X	XX	XX.X	xx	XX.X
Early Termination / Reason								
Any reason	xx	XX.X	xx	XX.X	XX	XX.X	xx	xx.x
SAE (other than death)								
AE (other than SAE)								
Lost to follow-up								
Non-compliance / protocol deviation								
Voluntary withdrawal								
Withdrawn by investigator								
Termination of site or study by sponsor								
Death								
Enrolled but not vaccinated								
Other								

N=Number of participants enrolled in the study.

<sup>a Refer to Listing 16.2.1 for reasons participants discontinued or terminated early.

<sup>b Refer to Listing 16.2.3 for reasons participants are excluded from the immunogenicity analysis.

TABLE 14.1.4.1: Summary of Demographic and Baseline Characteristics by Treatment Group - Full Analysis Population

Statistic	Adjuvanted MCV-5 (N=X)	Non-adjuvanted MCV-5 (N=X)	Menactra® (N=X)	All Participants (N=X)
Sex, n (%)				
Male	x (x.x)	x (x.x)	x (x.x)	x (x.x)
Female	x (x.x)	x (x.x)	x (x.x)	x (x.x)
Ethnicity, n (%)				
Not Hispanic or Latino	x (x.x)	x (x.x)	x (x.x)	x (x.x)
Hispanic or Latino	x (x.x)	x (x.x)	x (x.x)	x (x.x)
Not Reported	x (x.x)	x (x.x)	x (x.x)	x (x.x)
Unknown	x (x.x)	x (x.x)	x (x.x)	x (x.x)
Race, n (%)				
American Indian or Alaskan Native	x (x.x)	x (x.x)	x (x.x)	x (x.x)
Asian	x (x.x)	x (x.x)	x (x.x)	x (x.x)
Native Hawaiian or Other Pacific Islander	x (x.x)	x (x.x)	x (x.x)	x (x.x)
Black or African American	x (x.x)	x (x.x)	x (x.x)	x (x.x)
White	x (x.x)	x (x.x)	x (x.x)	x (x.x)
Age (years)				
Mean (SD)	x.x	x.x	X.X	x.x
Median	x.xx	x.xx	X.XX	x.xx
IQR	х	х	X	х
Range	x.x	x.x	X.X	x.x
Height (cm)	·			
Mean (SD)	X.X	X.X	X.X	x.x
Median	x.xx	x.xx	X.XX	x.xx
IQR	х	х	X	х
Range	X.X	X.X	X.X	X.X
Weight (kg)				
Mean (SD)	X.X	x.x	X.X	X.X
Median	X.XX	x.xx	X.XX	X.XX
IQR	X	х	X	Х
Range	X.X	X.X	X.X	X.X

N = Number of participants in the Full Analysis population. n = Number of participants reporting the response.

TABLE 14.1.4.2: Summary of Demographic and Baseline Characteristics by Treatment Group - Per-Protocol Population

Statistic	Adjuvanted MCV-5 (N=X)	Non-adjuvanted MCV-5 (N=X)	Menactra® (N=X)	All Participants (N=X)
Sex, n (%)				
Male	x (x.x)	x (x.x)	x (x.x)	x (x.x)
Female	x (x.x)	x (x.x)	x (x.x)	x (x.x)
Ethnicity, n (%)				
Not Hispanic or Latino	x (x.x)	x (x.x)	x (x.x)	x (x.x)
Hispanic or Latino	x (x.x)	x (x.x)	x (x.x)	x (x.x)
Not Reported	x (x.x)	x (x.x)	x (x.x)	x (x.x)
Unknown	x (x.x)	x (x.x)	x (x.x)	x (x.x)
Race, n (%)				
American Indian or Alaskan Native	x (x.x)	x (x.x)	x (x.x)	x (x.x)
Asian	x (x.x)	x (x.x)	x (x.x)	x (x.x)
Native Hawaiian or Other Pacific Islander	x (x.x)	x (x.x)	x (x.x)	x (x.x)
Black or African American	x (x.x)	x (x.x)	x (x.x)	x (x.x)
White	x (x.x)	x (x.x)	x (x.x)	x (x.x)
Age (years)				
Mean (SD)	x.x	x.x	X.X	x.x
Median	x.xx	x.xx	X.XX	x.xx
IQR	х	x	X	х
Range	x.x	x.x	X.X	x.x
Height (cm)	·			
Mean (SD)	X.X	X.X	X.X	x.x
Median	x.xx	x.xx	X.XX	x.xx
IQR	х	х	X	х
Range	X.X	X.X	X.X	X.X
Weight (kg)				
Mean (SD)	X.X	x.x	X.X	X.X
Median	X.XX	x.xx	X.XX	X.XX
IQR	X	х	X	Х
Range	X.X	X.X	X.X	X.X

N = Number of participants in the Full Analysis population. n = Number of participants with a response.

TABLE 14.1.5.1: Summary of Pre-Existing Medical Conditions by Treatment Group - Full Analysis Population

	Adjuvanted MCV-5 (N=X)		]	adjuvanted MCV-5 (N=X)		enactra® (N=X)	All Participants (N=X)		
	n	%	n	%	n	%	n	%	
Medical Problem	XX	xx.x	XX	xx.x	XX	xx.x	XX	xx.x	
Head	XX	XX.X	XX	XX.X	XX	xx.x	XX	XX.X	
Eyes	XX	xx.x	XX	XX.X	XX	xx.x	XX	XX.X	
Ears	XX	XX.X	XX	xx.x	XX	xx.x	XX	XX.X	
Nose									
Throat/Mouth									
Cardiovascular									
Heart/Veins or Arteries									
Respiratory									
Gastrointestinal									
Stomach									
Intestines									
Etc.									

N= Number of participants in the Full Analysis population; n= Number of participants reporting medical history within the specified SOC. A participant is only counted once per SOC.

TABLE 14.1.5.2: Summary of Pre-Existing Medical Conditions by Treatment Group - Per-Protocol Population

As above

